Protocol Title:
**Meditation and Yoga for Heightened Anxiety
related to COVID-19**

Version Date:
12/19/2023

Protocol Number:
7987

First Approval:
04/27/2020

Research Area:
Anxiety, Mood, Eating & Related Disorders

Expiration Date:
No Expiration

Division:
Anxiety/PTSD/OCD

Contact Principal Investigator:
[name]
Email: **[contact]**
[contact]**

Co-Investigator(s):
[name]

Research Chief:
[name]

Annual Progress

Current Status of Study

Current Status of Study

Only data analysis is ongoing

Number of participants currently enrolled:

0

Is NYSPI-IRB the IRB of record? If No, specify the IRB of record and, if applicable, provide a copy of the most recent approval notice.

Yes

Confirmations:

- ✓ Confirm there have been no un-reported serious adverse events (SAEs)
- ✓ Confirm there have been no unapproved modifications

Total Number of participants enrolled to date:

256

Summary

Have there been any study findings, recent literature, or untoward events occurring here or at other sites in the past year which might affect the analysis of the safety, risks or benefits of study participation?

No

Confirm that all study staff with a significant role in the design or implementation of the human subject components of this study has completed required training in human research subject protections.

✓ Yes

Overall Progress

Approved sample size:

450

Total number of participants enrolled to date:

256

Number of participants who have completed the study to date:

256

Has the drop-out/withdrawal rate been significant?

Yes

There was sizeable dropout by week 2. Of the 256 who were randomized, by the end of the first two weeks, the drop-out rate was 49% for psychoeducation alone, 52% for psychoeducation plus meditation, and 69% for psychoeducation and Kundalini yoga (calculated based on the number of participants who completed at least one questionnaire by the end of the week 2). By the end of the treatment period in the study (week 8) the drop-out was 71% for psychoeducation alone, 72% for psychoeducation plus meditation, and 84% for psychoeducation and Kundalini yoga.

Comments / Additional Information

N/A

Procedures

To create the protocol summary form, first indicate if this research will include any of the following procedures

- ✓ Somatic Treatment or Intervention
- ✓ Internet-based Data Collection or Transmission

Population

Indicate which of the following populations will be included in this research

- ✓ Medically Ill Subjects
- ✓ Adults

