Guided Meditation. This lasts 11 minutes. It is composed of words spoken over a musical background. In this meditation the subjects are guided to picture a healing force or light, a positive energy field, circulating around and within and through themselves. When this force comes in contact with areas that are troubled or painful, subjects are instructed to visualize the distress as being transformed such that healing takes place. They will complete the 25 minutes of stretching/meditation each day. Each week they will watch a new informational talk on Kundalini yoga. Participants will be asked to maintain a meditation log throughout the 8 weeks. They will be asked to record the number of minutes of meditation and stretching as well as any discomfort they experienced. They will also fill out questionnaires at weeks 2, 4, 6, 8 and at 3- and 6-months post-treatment.

Study Drop-outs. Participants are free to drop-out of the study at any time. We will ask participants in the consent form to complete a set of assessments at the time point that they discontinue from the study and also complete a questionnaire indicating the reason for dropping out.

3-Month and 6-Month Follow-ups. All participants will be asked to complete a follow-up set of assessments at 3- and 6-months post-treatment which will allow us to determine whether treatment gains at week 8 have been sustained and whether the meditation or yoga practice has been continued. The study will not impose any restrictions on the participants after week 8. In other words, participants are then free to pursue other interventions if they wish.

After a study is closed to new enrollment, a feedback questionnaire will be sent to all study participants. The feedback questionnaire consists of two parts:

- **the Treatment Satisfaction Questionnaire (3 questions) and**
- **6 questions about participant's decision to discontinue the study.**

Overall, it takes less than 3 minutes to complete the questionnaire. Participants may choose not to answer any of the questions. Neither of the questions requires to disclose any personal information.

Contact with our research team:

- a. For study-related questions, participants will be able to reach our study coordinator through Proofpilot or through email to our study coordinator
 - b. For clinical emergencies, as described in the consent form, participants should go to the nearest emergency room or be evaluated by their current doctor.

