 - c. Should the clinical assessment of depression after randomization indicate a rating in the severe range, an automatic email will be sent to the study coordinator and members of the team notifying them of the participant's high score. The study coordinator will then email the participant and recommend an evaluation by a local mental health provider. The patient will be asked to complete a follow-up depression rating 2 weeks later. If the score again falls in the severe range, one of our study clinicians will attempt to contact the patient by email or phone to recommend evaluation by a local mental health provider and to discuss withdrawal from the study. Withdrawal from the study will be determined according to the clinician's judgement after speaking with the participant, and assessing the costs/benefits to the participant of continuing with the intervention. This does not preclude the clinician from also making referrals or recommendations regarding additional treatment.
- You can upload charts or diagrams if any

Criteria for Early Discontinuation

Criteria for Early Discontinuation

Participants who develop severe depression during the course of this study that persists on the PHQ8 measure for 2 consecutive assessments will be discontinued from the study if appropriate based on clinical judgement. The patient will be contacted by one of the study physicians either by phone (or email). During this contact the physician will recommend referral to a local mental health provider. The study physician will speak with the participant at this time to determine whether it is in the best interests of the participant to remain in or be withdrawn from the study. Significant worsening of depression will be operationalized as a PHQ8 score (20 or higher) that falls in the severe range on 2 consecutive 1-week ratings.

Assessment Instruments

Create a table or give a brief description of the instruments that will be used for assessment

Measure	# of items	Screen	Baseline	Week 2	Week 4	Week 6	Week 8	3-month FU	6-month FU
COVID-19 exposure/status	2	X							
CRISIS Survey Baseline and Follow-up 3.0	10-30		X	X	X	X	X	X	X
GAD-7	7	X	X	X	X	X	X	X	X
Whiteley 8	8		X	X	X	X	X	X	X
SSS-8	8		X		X		X	X	X
PROMIS Sleep	4		X		X		X	X	X

Disturbance							
Emotion Regulation Questionnaire	10		X	X	X	X	X
Neuro-QOL - Applied Cognition	8		X	X	X	X	X
PHQ-8	8	X	X	X	X	X	X
Brief Hypervigilance Scale	5		X	X	X	X	X
Intolerance of Uncertainty Scale	12		X	X	X	X	X

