Upload copy(ies) of bolded Consent Form(s)

Upload copy(ies) of recruitment materials/ads to be reviewed

Upload copy(ies) of the HIPAA form

HIPAA Waiver-alteration of consent_2020-04-21_CB.pdf

HIPAA consent_2020-04-24.pdf

Upload any additional documents that may be related to this study

Post_Study_Feedback_Questionnaire_4.6.2021.pdf

Statistician	Data preparation and analysis is performed by a research scientist for the team.
Study Objectives	
The primary purpose of this study is to determine whether heightened anxiety in the context of COVID-19 can be reduced through web-based interventions.
 
This randomized clinical on-line study will examine whether a daily practice of meditation or Kundalini Yoga with anxiety reduction training leads to a greater reduction in anxiety than anxiety reduction training alone.

Primary endpoint	Week 8 evaluation.
Study Design	
This randomized on-line study is for individuals with anxiety and distress triggered by COVID-19 who have not yet been infected with the novel corona virus.
 
The primary study goal is to examine the extent to which anxiety can be reduced through the use of on-line training programs. All participants will receive Anxiety Reduction Training using cognitive-behavioral methods known to be helpful in reducing stress, anxiety, depression, and insomnia. In addition, two-thirds of participants will be randomly assigned to receive training in either Kundalini Yoga (KY) or mindfulness meditation. The investigators will assess the degree to which each of these training programs lead to reduced stress, improved well-being, decreased multisystem symptoms, enhanced mood, and reduced cognitive complaints. Participants will complete self-report assessments at 2-week intervals during the 8 weeks of the acute phase of the study and then again 3- and 6-months later. For details see PSF.

General Study Population	See PSF respective section
Inclusion-Exclusion Criteria	See PSF respective section
Study Assessments	See PSF respective section
Sample size	The study enrollment was closed in 2022 with a sample size of 256.
Randomization	Randomization will be a simple allocation with 1:1:1 ratio. Participants will be randomly assigned to one of three groups: a) Meditation (using Journey meditation) with psychoeducation; b) Kundalini Yoga (provided through an on- line video program) with psychoeducation; or c) psychoeducation alone.

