Primary aim#1	Aim 1: Test whether Kundalini Yoga with psychoeducation results in a significantly greater reduction in anxiety and multi-system symptom severity compared to psychoeducation alone.
Primary aim #2	Aim 2: Test whether a mindfulness meditation practice with psychoeducation leads to a significantly greater reduction in anxiety and multi-system symptom severity compared to psychoeducation alone.
Secondary aims and Exploratory goals:	
Aim 3: To assess whether treatment outcomes are moderated by COVID-19 related variables and personal variables.
 
Aim 4: To assess at the follow-up at month 3 whether patients have continued with the meditation practice and whether gains observed at week 8 have been sustained.
 
Aim 5: To assess whether there is a difference in both primary and secondary outcomes between the Kundalini Yoga and the meditation treatment groups.

Timing of Analysis	Analysis will be performed after the study is stopped for enrollment and a year after to make sure that all participants have finished their participation.
Analysis Population	We conduct analysis of a change score between baseline and week 8 for those who were randomized into one of the study arms and completed active treatment phase.
Missing Data	Missing data is treated as missing at random
Interim Analyses and Data Monitoring	There is no interim analysis for the protocol.
Primary aim#1 analysis	To investigate whether Kundalini Yoga with psychoeducation results in a significantly greater reduction in two primary outcome measures compared to psychoeducation alone, we will compare two groups of completers using one-sided t-test. P-value and estimation parameter value will be provided.
Primary aim#2 analysis	To investigate whether mindfulness meditation practice with psychoeducation leads to a significantly greater reduction in two primary outcome measures compared to psychoeducation alone, we will compare two groups of completers using one-sided t-test. P-value and estimation parameter value will be provided.

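### The SAP assumes missing at random but analyses completers only, which does not implement that assumption, with 71% to 84% drop-out by week 8 and no sensitivity analysis

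*Combined protocol and SAP*

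**What the plan says.** - **Missing data (SAP, Missing Data).** The entry is one sentence: "Missing data is treated as missing at random". It names no imputation or likelihood model, no conditioning variables and no sensitivity analysis.
- **Primary analysis (SAP, Primary endpoint, Analysis Population, and Primary aim#1 and #2 analysis).** The endpoint is the "Week 8 evaluation". Change from baseline is compared, yoga against psychoeducation and meditation against psychoeducation, by one-sided t-test. Only randomised participants who finished the active treatment phase are included. No significance level is given.
- **Numbers (SAP, Sample size and Randomization).** "The study enrollment was closed in 2022 with a sample size of 256"; "Randomization will be a simple allocation with 1:1:1 ratio". Arm sizes are not reported.
- **Drop-out (protocol, Overall Progress).** By week 2, "the drop-out rate was 49% for psychoeducation alone, 52% for psychoeducation plus meditation, and 69% for psychoeducation and Kundalini yoga". By week 8, "the drop-out was 71% for psychoeducation alone, 72% for psychoeducation plus meditation, and 84% for psychoeducation and Kundalini yoga".
- **Data that could inform the assumption (protocol, Study Procedures).** GAD-7 and Whiteley-8, listed there as the primary measures, are scheduled at baseline and weeks 2, 4, 6 and 8. Under Study Drop-outs, people who leave are to be asked to "complete a set of assessments at the time point that they discontinue from the study and also complete a questionnaire indicating the reason". A later feedback questionnaire has six questions on discontinuing. The SAP uses none of this.

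**The concern.** The stated assumption and the planned test do not match. Missing at random allows drop-out to depend on what was observed, such as baseline or week-2 scores, provided the analysis conditions on it. A t-test on completers' change scores conditions on nothing. It recovers the difference between the randomised arms only if leaving is unrelated to outcome within each arm, or if selection biases both arms equally.

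Neither condition can be taken for granted. The arms ask for different daily effort (none beyond handouts, 15 minutes of meditation, 25 minutes of yoga practice), so people may leave for different reasons. If yoga participants who are not improving leave and comparable control participants stay, the completer comparison favours yoga without any treatment effect.

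Moving to an all-randomised model would make the analysis agree with the stated assumption. That assumption would still be untested, with most week-8 outcomes unobserved.

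**Working it through.** **1. Amount missing.** Inputs: 256 randomised and the three week-8 rates. Equal arms are assumed: 256/3 = 85.3.

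| Arm | Drop-out, week 8 | Expected completers |
|---|---|---|
| Psychoeducation | 71% | 85.3 × 0.29 = 24.7 |
| Meditation | 72% | 85.3 × 0.28 = 23.9 |
| Yoga | 84% | 85.3 × 0.16 = 13.7 |

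The total is about 62, so 1 − 62.3/256 = 75.7% are missing. Over the 95% range of arm sizes that simple 1:1:1 allocation can produce, the figure is 75.0% to 76.4%. The documents give no pooled rate to compare with.

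**2. Where the imbalance lies** (85 per arm assumed).
- Yoga against psychoeducation, week 8: 71 against 60 lost, chi-square p = 0.045, Fisher p = 0.067. Week 2: 59 against 42, chi-square p = 0.008.
- Meditation against psychoeducation, week 8: 61 against 60, chi-square p = 0.87.

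**3. Timing.** Week-2 drop-out as a share of week-8 drop-out is 49/71 = 69% (psychoeducation), 52/72 = 72% (meditation) and 69/84 = 82% (yoga).

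**4. What the completer t-test does when data are missing at random.** This is an illustrative simulation with no true effect, 85 per arm, a correlation of 0.6 between week-2 and week-8 change, and a nominal one-sided level of 5%. Retention was 16% (yoga) and 29% (psychoeducation).

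| Retention depends on week-2 change | Bias of completer difference | Type I error |
|---|---|---|
| In neither arm | 0.00 SD | 5% |
| Equally in both (log-odds 0.5 to 1.0 per SD) | 0.04 to 0.09 SD | 7% to 8% |
| In yoga only (log-odds 0.5 to 1.0 per SD) | 0.24 to 0.45 SD | 17% to 35% |

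A regression on week-2 change was about unbiased in every row, but the simulation gave it every week-2 value. The trial will not have them all.

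**5. Departure from missing at random, all-randomised contrast.** Let delta be the amount by which drop-outs do worse than the model predicts.
- Active arm only: shift = (active drop-out) × delta. This is 0.84 × delta for yoga and 0.72 × delta for meditation.
- Same delta in both arms: shift = (active − control drop-out) × delta. This is (0.84 − 0.71) = 0.13 × delta for yoga and (0.72 − 0.71) = 0.01 × delta for meditation.

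Take an assumed contrast of 0.5 SD, since the documents give no effect size. With delta in the active arm only, it reaches zero at 0.5/0.84 = 0.60 SD (yoga) or 0.5/0.72 = 0.69 SD (meditation). With a common delta, it reaches zero at 0.5/0.13 = 3.8 SD or 0.5/0.01 = 50 SD.

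**The case against.** Several stronger readings are tempting, and the documents do not support them.

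- **That the unobserved participants dominate the planned estimate.** They have no weight in a completer t-test. The 0.84 and 0.72 shifts belong to an all-randomised contrast, which the SAP does not define, so the sensitivity analysis presupposes a change to the main analysis.
- **That drop-out is unequal throughout.** Meditation and psychoeducation differ by one percentage point.
- **That any modest departure would overturn a result.** This holds only if drop-outs do worse in the active arm alone. A common departure hardly matters. Nor would the 0.5 SD example be significant for yoga to begin with: with 25 and 14 completers, one-sided 5% (assumed) requires 1.69 × √(1/25 + 1/14) = 0.56 SD. The delta at which significance is lost can be found only from the data.
- **That the plan itself shows missing at random to be false.** After repeated severe depression scores, "Withdrawal from the study will be determined according to the" study clinician's view following a conversation. The trigger is a recorded PHQ-8 score, and scores of 20 or more are excluded at entry. With the full battery at week 4 and a repeat two weeks later, this route could hardly act before about week 6, whereas most loss had occurred by week 2. No count of such withdrawals is given.
- **That the drop-out data are in hand.** The protocol says that they will be requested. How much was obtained is not stated.

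These objections limit the size and certainty of the concern. They leave standing the mismatch between assumption and test, and the absence of any sensitivity analysis.

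**Conclusion.** The point holds in limited form. The SAP names missing at random but plans an analysis that needs a stronger condition, and it has no means of showing how far a conclusion depends on either. With about 76% of week-8 outcomes missing, following the plan as written can give a biased answer. The documents do not settle the direction or the size of that bias.

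For yoga (Aim 1), both the amount missing and the unequal rates matter. For meditation (Aim 2), only the amount and possibly different reasons for leaving matter.

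The figures assume near-equal arms and read drop-out as a missing week-8 assessment. The SD-scaled results, the simulation settings and the one-sided 5% level are illustrative. Overall Progress also counts all 256 as having completed the study. That fits the drop-out rates only if it means that participation has ended, so the SAP should define completion of the treatment phase.

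**What to change.** 1. Make the main analysis an all-randomised model valid under missing at random, such as a likelihood-based repeated-measures model or multiple imputation. Use baseline, weeks 2, 4 and 6, and any discontinuation assessment actually obtained. State the significance level.
2. Add a delta-adjusted multiple-imputation sensitivity analysis for both GAD-7 and Whiteley-8. Fix and date the delta grid before arm results are seen, for example 0 to 1 baseline SD of each measure. Apply it to active-arm drop-outs alone and then to drop-outs in both arms.
3. Report, for each contrast and measure, the delta at which any significant result is lost, so that readers can judge its plausibility.
4. Tabulate the available reasons for drop-out by arm, with the number of participants who gave none.

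**Cost.** A short SAP revision and extra analysis work, with no new data collection. A favourable result may have to be stated less strongly. If most early drop-outs have no score after baseline, the imputation will rest largely on baseline, and the report should say so. Data analysis is already under way, so the change must be dated and labelled as a late addition.

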The psychoeducation component received by all participants educates about the impact of anxiety on the body and how our thoughts, feelings, and behaviors can be modified to reduce anxiety. Kundalini Yoga consists of breathing, meditation, and stretching techniques. The guided meditation includes breathing and mindfulness training delivered online. We plan to assess the extent to which these two mind-body practices can augment the psychoeducation in reducing anxiety. The primary outcomes will be improvement in self-reported anxiety and in self-reported multisystem symptom severity. Secondary outcomes will assess cognitive complaints, depression, sleep, and fatigue.

This will be an on-line study. During this study, patients will be screened through an on-line process, review consent, and complete self-report questionnaires. 450 patients will be enrolled. Of these, 150 will be randomly assigned to kundalini yoga with psychoeducation, 150 will be assigned to mindfulness meditation with psychoeducation, and 150 will be assigned to psychoeducation alone. Assessments will be conducted weekly to 8 weeks; there will also be a 3- and 6-month follow-up by questionnaire. All participants at the end of the 8 weeks will be offered the option of receiving an additional 8 weeks of free access to meditation recordings through Journey meditation which provide guided meditation. For follow-up purposes, we will collect information on any/all treatments (e.g., psychopharmacological, psychotherapeutic, mind-body therapies) that participants have engaged in during the post-treatment phase to control for this at the analysis stage.

Should this study find evidence suggesting that either meditation therapy with psychoeducation and/or Kundalini Yoga with psychoeducation delivered remotely contribute additional benefit beyond psychoeducation alone in augmenting anxiety reduction, this would be a valuable and welcome research finding that would have broad public health implications as it provides patients in the time of a public health crisis with a beneficial new approach to addressing anxiety.

Background, Significance and Rationale

Background, Significance and Rationale

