Our expectation is that many patients will benefit in this study, regardless of the treatment received, as everyone will be receiving psychoeducation. Our primary hypothesis: Among participants with heightened anxiety in the context of an infection pandemic (COVID-19), augmentation of psychoeducation with Kundalini Yoga or Meditation will lead to a greater reduction in anxiety and in severity of multi-system

symptoms than treatment with psychoeducation alone.

SPECIFIC AIMS

Aim 1: Test whether Kundalini Yoga with psychoeducation results in a significantly greater reduction in anxiety and multi-system symptom severity and in improvement in secondary outcomes (e.g., depression, sleep, illness anxiety, fatigue, cognition) compared to psychoeducation alone

Aim 2: Test whether a mindfulness meditation practice with psychoeducation leads to a significantly greater reduction in anxiety and multi-system symptom severity and in improvement in secondary outcomes (e.g., as above) compared to psychoeducation alone

Aim 3: To assess whether treatment outcomes are moderated by COVID-19 related variables (e.g., health/COVID exposure status, impact on job/school/financial stability) and personal variables (e.g, prior health status, substance use, intolerance of uncertainty, social support network, spirituality/religiosity)

Aim 4: To assess at the follow-up at month 3 whether patients have continued with the meditation practice and whether gains observed at week 8 have been sustained.

Aim 5: To assess whether there is a difference in both primary and secondary outcomes between the Kundalini Yoga and the meditation treatment groups.

Description of Subject Population

Sample #1

Specify subject population

Individuals with heightened anxiety

Number of completers required to accomplish study aims

270

Projected number of subjects who will be enrolled to obtain required number of completers

360

Age range of subject population

18-70

Gender, Racial and Ethnic Breakdown

Our Estimates are based on nationwide surveys of meditation practice conducted by the Pew Research Center

<https://www.pewforum.org/religious-landscape-study/frequency-of-meditation/#demographic-information>

Based on the Pew publications of the U.S. Population, we anticipate the following gender and racial/ethnic

group representation

Gender: 50% women, 50% men

Racial/ethnic: 60% Caucasian, 15% Black, 18% Latino, and 7% other

Description of subject population

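### The four one-sided primary tests have no stated alpha, success rule, multiplicity control or confidence interval, and the second primary outcome is defined in conflicting ways

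*Combined protocol and SAP*

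**What the plan says.** The SAP rows Primary aim#1 analysis and Primary aim#2 analysis share one design. For yoga, and then for meditation, each against psychoeducation alone, "we will compare two groups of completers using one-sided t-test". Each row looks for a "significantly greater reduction in two primary outcome measures" and names neither measure. The only reporting rule is "P-value and estimation parameter value will be provided". The Analysis Population row limits the comparison to change from baseline to week 8 in "those who were randomized into one of the study arms and completed active treatment phase". No other section gives a significance level, test order, adjustment, success rule or interval.

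The wording about what would count as success varies:
- The aims, in the protocol and in the SAP, join anxiety and multi-system symptom severity with *and*.
- The protocol's primary hypothesis puts *or* between the practices: "augmentation of psychoeducation with Kundalini Yoga or Meditation will lead to a greater reduction in anxiety", followed by symptom severity.
- The SAP's Study Objectives row mentions anxiety only: the question is whether practice "leads to a greater reduction in anxiety than anxiety reduction training alone".

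The second primary outcome is described in two ways:
- The Lay Summary gives the primary outcomes as "improvement in self-reported anxiety and in self-reported multisystem symptom severity". The Background section, the Specific Aims and the SAP aims use the same construct. Aim 1 in the protocol puts illness anxiety among the secondary outcomes: "in improvement in secondary outcomes (e.g., depression, sleep, illness anxiety, fatigue, cognition".
- The outcome list under Study Procedures names GAD-7 and Whiteley-8 as primary and places SSS-8 among the secondary measures. The schedule under Assessment Instruments fits that list. During treatment, GAD-7 and Whiteley-8 are collected at weeks 2, 4, 6 and 8, and SSS-8 only at weeks 4 and 8.

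**The concern.** The same four p-values can support different conclusions, depending on whether one outcome is enough, whether the two arms are judged together, and which alpha applies. None of this is written down. The Annual Progress section reports that the study has reached the data-analysis stage, so these choices may be made with results in view.

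The conflict over the second outcome is a separate error. The construct in the aims (symptoms across body systems) is not what Whiteley-8 is listed as measuring (health anxiety), and the somatic scale is listed as secondary.

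Reporting is also thin for groups that may be small. A one-sided test does not examine worsening, which the protocol's own risk section says is possible. A two-sided interval would show precision and direction together.

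**Working it through.** **No figure to reproduce.** The documents give no alpha, power, effect size or standard deviation. The check is therefore conditional on stated assumptions.

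**Inputs**
- Tests: 2 practices × 2 outcomes = 4, with a shared control (SAP analysis rows).
- Alpha: one-sided 0.05 assumed, with 0.025 as the alternative.
- Correlation ρ between the two outcomes: not given; varied from 0 to 0.9.
- Completers: arm sizes are not given. An equal split of 256 is 85.3 per arm. With the week-8 dropout of 71%, 72% and 84% from Annual Progress: 85.3 × 0.29 = 24.7 control, 85.3 × 0.28 = 23.9 meditation, 85.3 × 0.16 = 13.7 yoga, or about 25/24/14.

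**Correlation between the two comparisons, from the shared control**
r = √[nM/(nM + n0) × nK/(nK + n0)] = √[23.9/48.6 × 13.7/38.4] ≈ 0.418. Here n0, nM and nK are the control, meditation and yoga completers.

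**False benefit when nothing works**
- Any of four = 1 − Φ₄(c, c, c, c; R), where c = 1.645 and R is the Kronecker product of the 2 × 2 matrices with off-diagonals r and ρ.
- Both outcomes in at least one arm: simulated from the same distribution.
- Either outcome within one arm (meditation): simulated pooled t-tests at 25/24. At ρ = 0 the theoretical value is 1 − 0.95² = 9.75%.

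| Rule | ρ = 0 | 0.3 | 0.5 | 0.7 | 0.9 |
|---|---|---|---|---|---|
| Either outcome, one arm, 0.05 | 9.6% | 9.4% | 8.8% | 8.2% | 6.9% |
| Any of four, both arms, 0.05 | 17.2% | 16.3% | 15.4% | 14.2% | 12.1% |
| Both outcomes within an arm, either arm, 0.05 | 0.5% | 1.4% | 2.3% | 3.7% | 5.9% |
| Any of four, both arms, 0.025 | 9.1% | 8.7% | 8.3% | 7.6% | 6.5% |

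Hand check at ρ = 0: one outcome tested in both arms gives 9.01%, so two independent outcomes give 1 − (1 − 0.0901)² = 17.2%.

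**Effect of the rule alone.** Correlation belongs to the data and is not a choice, so rules should be compared at a fixed ρ. At ρ = 0.7 the two-arm figure moves from 3.7% (both required) to 14.2% (any of four).

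**Sensitivity to completer counts.** In t-test simulations, any-of-four runs from 17.3% to 12.1% at 12/12/7 and from 17.1% to 12.1% at 37/36/21. The counts hardly matter for this error rate.

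**Ordered test (GAD-7, then the second outcome) at one-sided 0.05.** Over eight patterns of true and null effects and four correlations, the simulated error within an arm was 4.8–5.2%. Across both arms it is 9.0% when nothing works, because only GAD-7 can open a claim, and at most 9.9% over the patterns.

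**The both-outcomes rule is not always as strict as its row in the table.** If one outcome truly improves in each arm and the other does not, its two-arm error is about 9–10%.

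**The case against.** The strongest reply is that the plan already implies a strict rule. The aims join the outcomes with *and*, so both are needed, and the two-arm figure is then 0.5–6% when nothing works. A reader might infer instead that any one of four wins would count, and so take 12–17% as the trial's error rate. No section says so. The two practices are separately numbered aims, and joint control over separate arms is debated. This stands as a limit on the size of the point. It does not remove it, because an aim is not a decision rule, and the *or* in the hypothesis and the anxiety-only objective are no clearer. The objective should not be pressed either: the SAP's Study Design row does mention multisystem symptoms.

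A reader might also infer that the second outcome is open, to be picked later from Whiteley-8 and SSS-8, and add those extra tests to the error. The documents do not support that. The outcome list is the only place that names primary instruments, it names two, and the assessment schedule agrees with it. What remains is a conflict of label and construct.

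Nor does a missing interval hide precision altogether. If the reported estimate is the mean difference, its p-value and the group sizes return the standard error, apart from rounding. The absence is a reporting gap.

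Finally, the Lay Summary and the SAP aims give the two outcomes equal standing, so putting GAD-7 first is a choice the documents do not make. It is also looser than the both-outcomes rule when nothing works. Both remarks are right and are carried into the fix.

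**Conclusion.** The point holds. Alpha, success rule, multiplicity control and intervals are absent, and the second primary outcome is contradictory as written.

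The within-arm figure of about 7–10%, against a nominal 5%, is the firmest measure of what is at stake, and it applies only if either outcome may support a claim. The 12–17% figure needs the further assumption that any of four tests counts. At one-sided 0.025 it would be 6–9%.

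All figures rest on an assumed alpha, a range of outcome correlations and normally distributed outcomes. They cover multiplicity only and assume no bias from analysing completers. The counts of 25/24/14 are an assumption too: Annual Progress defines its dropout calculation only for week 2, and the SAP does not define completion of the treatment phase.

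**What to change.** 1. **Outcome.** Reconcile the Lay Summary, Background, Specific Aims and SAP aims with the outcome list and the assessment schedule, and name the two primary instruments in the SAP. Cost: wording only.
2. **Alpha and intervals.** State the alpha and report a two-sided 95% confidence interval for every primary comparison. If one-sided 0.05 is kept, say so beside the interval, because a 95% interval can then include zero when the test is significant. Cost: extra output.
3. **One success rule per arm.** Choose one of:
   - Require both outcomes, as the *and* in the aims reads. This is the stricter rule when nothing works. Its power cannot exceed that of either test alone; the documents give no effect sizes from which to compute the loss.
   - If a single outcome may support a claim, test GAD-7 first, and the second outcome only if GAD-7 is significant. GAD-7 is the undisputed primary measure and the entry measure. It loses no power: at 25/24/14 the effect detectable with 80% power stays at 0.72 SD (meditation) and 0.85 SD (yoga) at one-sided 0.05. From half to 1.5 times those completers, these run from 1.05 to 0.59 SD and from 1.23 to 0.69 SD. The price is that the second outcome cannot be claimed alone. This is stricter than letting either outcome count and looser than requiring both, and about 9–10% remains across the two arms.
4. **Optional control across arms, with the ordered test.** Use one-sided 0.025 per arm, and pass an arm's share to the other only after both of its outcomes are rejected. Simulated two-arm error is then 4.5–5.1%. Detectable effects rise to 0.82 and 0.96 SD, and power at the effects in step 3 falls from 80% to about 69–70%.

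Label any of these choices post hoc if results are already known.
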